#### 10.3.2.3. Vital Signs

Vital signs (BP and pulse) and body temperature will be measured (sitting) after resting for a minimum of 10 minutes at times indicated in the Study Schedule ([Attachment 1](#)). At baseline (Week 0; Visit 2) and Week 12 (Visit 7), BP and pulse should be measured prior to administration of the investigational product and again approximately 1 hour post administration. Any clinically significant findings that result in a diagnosis should be captured on the eCRF. Additional measurements of vital signs may be performed at the discretion of the investigator.

#### 10.3.2.4. Electrocardiograms

For each patient, 12-lead digital ECGs will be obtained locally as single ECGs according to the Study Schedule ([Attachment 1](#)). Patients must be supine for approximately 5 to 10 minutes before ECG collection and remain supine but awake during ECG collection. Electrocardiograms may be obtained at additional times, when deemed clinically necessary. Collection of more ECGs than expected at a particular time point is allowed when needed to ensure high quality records.

Electrocardiograms will be interpreted by a qualified physician (the investigator or qualified designee) at the site as soon after the time of ECG collection as possible, and ideally while the patient is still present, and for immediate patient management, should any clinically relevant findings be identified. The qualified physician must document his/her review of the ECG at the time of evaluation. Any clinically significant findings that result in a diagnosis should be captured on the eCRF.

The ECGs will be maintained at the site and made available to the sponsor as requested.

#### **10.3.2.5. Immunogenicity**

Samples for immunogenicity testing will be collected at time points indicated in the Study Schedule ([Attachment 1](#)) and for any event judged by the investigator to be a potential systemic allergic reaction/hypersensitivity, when possible. Venous blood samples will be collected into tubes and used to determine antibody production against ixekizumab. The actual date of each sampling will be recorded on the laboratory requisition.

Immunogenicity will be assessed by a validated assay designed to perform in the presence of ixekizumab. Antibodies may be further characterized and/or evaluated for their ability to neutralize the activity of ixekizumab. Treatment-emergent immunogenicity is defined as any occurrence of a 4-fold or 2 dilution increase in titer over the pre-treatment baseline titer. In the case of a negative result at baseline, treatment-emergent immunogenicity is defined as an increase in titer to  $\geq 1:10$ . Blood samples are also being collected to determine serum ixekizumab concentration at same time as immunogenicity samples to facilitate interpretation of immunogenicity data (Section [10.4.2](#)). Samples may be stored for a maximum of 15 years following last patient visit to enable further analysis of immune responses to ixekizumab. The duration allows the sponsor to respond to regulatory requests related to the investigational product.

#### **10.3.2.6. Safety-Related Immune Markers**

IL-17 is believed to play a role in neutrophil homeostasis and in neutrophil-dependent host defense against extracellular infections (Happel et al. 2003; Huang et al. 2004; Milner et al. 2008). Neutrophil counts will therefore serve as a safety marker in the current investigation.

Ixekizumab is not expected to affect the numbers of B, T, and natural killer (NK) lymphocytes or serum immunoglobulin subclasses A, G, and M (IgA, IgG, and immunoglobulin M [IgM], respectively) in peripheral blood. However, since this is a novel immunomodulatory drug, these parameters will be measured in patients.

#### **10.3.2.7. Quick Inventory of Depressive Symptomatology-Self Report**

QIDS-SR16 is a self-administered, 16-item instrument intended to assess the existence and severity of symptoms of depression as listed in the American Psychiatric Association's Diagnostic and Statistical Manual of Mental Disorders, 4th Edition (DSM-IV) (APA 1994). The QIDS-SR16 scale is used to assess the potential impact of treatment on new onset or changes in depression, thoughts of death, and/or suicidal ideation severity. A patient is asked to consider each statement as it relates to the way they have felt for the past 7 days. There is a 4-point scale for each item ranging from 0 to 3. The 16 items corresponding to 9 depression domains are

summed to give a single score ranging from 0 to 27, with higher scores denoting greater symptom severity. The domains assessed by the instrument include: (1) sad mood, (2) concentration, (3) self-criticism, (4) suicidal ideation, (5) interest, (6) energy/fatigue, (7) sleep disturbance (initial, middle, and late insomnia or hypersomnia), (8) decrease/increase in appetite/weight, and (9) psychomotor agitation/retardation. Additional information and the QIDS-SR16 questions may be found at the University of Pittsburgh IDS/QIDS internet page [WWW]. A QIDS-SR16 assessment will be taken at times indicated in the Study Schedule ([Attachment 1](#)).

#### **10.3.2.8. Columbia-Suicide Severity Rating Scale**

The C-SSRS (Posner et al. 2007a, 2007b; Columbia University Medical Center [WWW]) is a scale that captures the occurrence, severity, and frequency of suicide-related ideations and behaviors during the assessment period. The C-SSRS must be administered by appropriately trained site personnel. The tool was developed by the National Institute of Mental Health Treatment of Adolescent Suicide Attempters trial group for the purpose of being a counterpart to the Columbia Classification Algorithm of Suicide Assessment (C-CASA) categorization of suicidal events. Patients will be assessed according to the Study Schedule ([Attachment 1](#)).

The Self-Harm Supplement Form is a one-question form that asks for the number of suicidal or nonsuicidal self-injurious behaviors the patient has experienced since the last assessment. For each unique event identified, a questionnaire (Self-Harm Follow-Up Form) which collects supplemental information on the self-injurious behavior is to be completed. This information is then documented in the eCRF. The Self-Harm Supplement Form will be completed according to the Study Schedule ([Attachment 1](#)).

#### **10.3.3. Safety Monitoring**

Lilly will periodically review evolving aggregate safety data within the study by appropriate methods.

In the event that safety monitoring uncovers an issue that needs to be addressed by unblinding at the group level, only members of the DMC (an advisory group for this study formed to protect the integrity of data [refer to Section [12.2.10.1](#)]) can conduct additional analyses of the safety data.

The Lilly CRP/CRS will monitor safety data throughout the course of the study and will, as is appropriate, consult with the functionally independent Global Patient Safety therapeutic area physician or clinical scientist.

The sponsor will review SAEs within time frames mandated by company procedures and will review trends, laboratory analytes, and AEs at periodic intervals.

See Section [8.3](#) for discontinuation criteria related to specific AEs and Sections [10.3.3.1](#), [10.3.3.2](#), [10.3.3.3](#), and [10.3.3.4](#) for the monitoring of neutropenia, hepatic injury, hepatitis B, and hypertension, respectively.

Vital signs will be monitored pre- and post-dose as indicated in the Study Schedule ([Attachment 1](#)).

### 10.3.3.1. Neutropenia

Patients with neutrophil counts  $<1500$  cells/ $\mu\text{L}$  should be managed for neutropenia as follows:

- $<500$  cells/ $\mu\text{L}$  ( $<0.50 \times 10^3/\mu\text{L}$  or  $<0.50$  GI/L), see Discontinuation Criteria (Section [8.3.1.1](#))
- $\geq 500$  cells/ $\mu\text{L}$  and  $<1000$  cells/ $\mu\text{L}$  ( $\geq 0.50 \times 10^3/\mu\text{L}$  and  $<1.00 \times 10^3/\mu\text{L}$  or  $\geq 0.50$  GI/L and  $<1.00$  GI/L), see Discontinuation Criteria (Section [8.3.1.1](#))
- $\geq 1000$  cells/ $\mu\text{L}$  and  $<1500$  cells/ $\mu\text{L}$  ( $\geq 1.00 \times 10^3/\mu\text{L}$  and  $<1.50 \times 10^3/\mu\text{L}$  or  $\geq 1.00$  GI/L and  $<1.50$  GI/L), and the patient has a concurrent infection that requires systemic anti-infective therapy (for example, antibiotic, antifungal agent, antiviral agent):
  - The dose of investigational product should be withheld, the patient should receive appropriate medical care, and a repeat test for neutrophil count should be performed within 4 weeks from knowledge of the initial report. If the repeat neutrophil count has returned to  $\geq 1500$  cells/ $\mu\text{L}$  ( $\geq 1.50 \times 10^3/\mu\text{L}$  or  $\geq 1.50$  GI/L) and the infection has resolved or is resolving, the patient may resume dosing of investigational product and evaluation at scheduled visits. If the neutrophil count remains  $\geq 1000$  cells/ $\mu\text{L}$  and  $<1500$  cells/ $\mu\text{L}$  ( $\geq 1.00 \times 10^3/\mu\text{L}$  and  $<1.50 \times 10^3/\mu\text{L}$  or  $\geq 1.00$  GI/L and  $<1.50$  GI/L), investigational product should continue to be withheld and a repeat neutrophil count should again be performed within another 4 weeks. If, after 2 repeat tests, the neutrophil count still remains  $\geq 1000$  cells/ $\mu\text{L}$  and  $<1500$  cells/ $\mu\text{L}$  ( $\geq 1.00 \times 10^3/\mu\text{L}$  and  $<1.50 \times 10^3/\mu\text{L}$  or  $\geq 1.00$  GI/L and  $<1.50$  GI/L), and:
    - a. the infection has not fully resolved, the patient will be discontinued from the study.
    - b. the infection has resolved, the patient may resume dosing and evaluation at scheduled visits. However, if resumption of dosing is not deemed appropriate by the investigator, the patient will be discontinued from the study.
- $\geq 1000$  cells/ $\mu\text{L}$  and  $<1500$  cells/ $\mu\text{L}$  ( $\geq 1.00 \times 10^3/\mu\text{L}$  and  $<1.50 \times 10^3/\mu\text{L}$  or  $\geq 1.00$  GI/L and  $<1.50$  GI/L), and the patient has no concurrent infection that requires systemic anti-infective therapy (for example, antibiotic, antifungal agent, antiviral agent):
  - Dosing may continue, and a repeat neutrophil count should be performed 4 to 8 weeks from knowledge of the initial report. Testing may be at a regularly scheduled visit or at an unscheduled visit, as necessary.

Repeat testing should be performed at 4- to 8-week intervals until the neutrophil count has returned to  $\geq 1500$  cells/ $\mu\text{L}$  ( $\geq 1.50 \times 10^3/\mu\text{L}$  or  $1.50$  GI/L). If the patient has 3 or more postbaseline neutrophil counts of  $\geq 1000$  cells/ $\mu\text{L}$  and  $<1500$  cells/ $\mu\text{L}$  ( $\geq 1.00 \times 10^3/\mu\text{L}$  and  $<1.50 \times 10^3/\mu\text{L}$  or  $\geq 1.00$  GI/L and  $<1.50$  GI/L), no value of  $<1000$  cells/ $\mu\text{L}$  ( $<1.00 \times 10^3/\mu\text{L}$  or  $<1.00$  GI/L), and no

post-baseline infection requiring systemic anti-infective therapy, the patient may continue or resume further evaluation at scheduled visits, as deemed appropriate by the investigator.

If a patient without initial concurrent infection develops an infection that requires systemic anti-infective therapy, then the patient should be managed as indicated above for patients with concurrent infection. Management of neutropenia during Period 4 is described in Section 7.1.4.1.

### 10.3.3.2. Hepatic Safety Monitoring

If a study patient experiences elevated ALT  $\geq 3X$  ULN, ALP  $\geq 2X$  ULN, or elevated TBL  $\geq 2X$  ULN, liver testing ([Attachment 3](#)) should be repeated within 3 to 5 days including ALT, AST, ALP, TBL, direct bilirubin, gamma-glutamyl transferase, and creatine kinase to confirm the abnormality and to determine if it is increasing or decreasing. If the abnormality persists or worsens, clinical and laboratory monitoring should be initiated by the investigator and in consultation with the study medical monitor. Monitoring of ALT, AST, TBL, and ALP should continue until levels normalize or return to approximate baseline levels.

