- Note: Determined by 2 consecutive elevated readings. If an initial BP reading exceeds this limit, the BP may be repeated once after the patient has rested sitting for  $\geq 10$  minutes. If the repeat value is less than the criterion limits, the second value may be accepted.

- [33] Are positive for human immunodeficiency virus serology (HIV; positive for human immunodeficiency virus antibody [HIVAb]).
- [34] Have evidence of or test positive for hepatitis B virus (HBV) by testing 1) positive for hepatitis B surface antigen (HBsAg+), OR 2) positive for anti-hepatitis B core antibody (HBcAb+) and are HBV deoxyribonucleic acid (DNA) positive.

Note: Patients who are HBcAb+ and HBV DNA negative may be enrolled in the study. Patients who meet these criteria at screening will be identified by the central laboratory as detailed in Section 10.3.3.3.

- [35] Have evidence of or test positive for hepatitis C virus (HCV). A positive test for HCV is defined as: 1) positive for hepatitis C antibody (anti-HCV Ab), and 2) positive via a confirmatory test for HCV (for example, HCV polymerase chain reaction).
- [36] Have clinical laboratory test results at screening that are outside the normal reference range for the population and are considered clinically significant per investigator assessment, and/or have any of the following specific abnormalities:
- [36a] Neutrophil count  $< 1500$  cells/ $\mu$ L ( $<1.50 \times 10^3/\mu$ L or  $<1.50$  GI/L)
  - [36b] Lymphocyte count  $< 500$  cells/ $\mu$ L ( $<0.50 \times 10^3/\mu$ L or  $<0.50$  GI/L)
  - [36c] Platelet count  $< 100,000$  cells/ $\mu$ L ( $<100 \times 10^3/\mu$ L or  $<100$  GI/L)
  - [36d] Aspartate aminotransferase (AST) or alanine aminotransferase (ALT)  $> 2.5$  times the upper limit of normal (ULN)
  - [36e] Total white blood cell (WBC) count  $<3000$  cells/ $\mu$ L ( $<3.00 \times 10^3/\mu$ L or  $<3.00$  GI/L)
  - [36f] Hemoglobin  $<8.5$  g/dL (85.0 g/L) for male patients and  $<8.0$  g/dL (80 g/L) for female patients
  - [36g] Serum creatinine  $>2.0$  mg/dL.

Note: The AST and ALT may be repeated once within a week if the initial response exceeds this limit, and the repeat value may be accepted if it is less than the criterion limits. Other laboratory tests should not be repeated unless there is a technical error or clinical reasons to believe a result may be erroneous.

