### **8.3.1. Discontinuation from Study Treatment**

#### **8.3.1.1. Permanent Discontinuation from Study Treatment**

- **Subject Decision**
  - The patient or the patient's designee, for example, parents or legal guardian requests to discontinue investigational product for any reason.
- Neutrophil (segmented) counts (see safety monitoring for neutropenia Section 10.3.3.1):
  - $<500$  cells/ $\mu\text{L}$  ( $<0.50 \times 10^3/\mu\text{L}$  or  $<0.50$  GI/L)
  - $\geq 500$  and  $<1000$  cells/ $\mu\text{L}$  ( $\geq 0.50 \times 10^3/\mu\text{L}$  and  $<1.00 \times 10^3/\mu\text{L}$  or  $\geq 0.50$  GI/L and  $<1.00$  GI/L) (based on 2 test results; the second test performed within 1 week from knowledge of the initial result).
  - $\geq 1000$  and  $<1500$  cells/ $\mu\text{L}$  ( $\geq 1.00 \times 10^3/\mu\text{L}$  and  $<1.50 \times 10^3/\mu\text{L}$  or  $\geq 1.00$  GI/L and  $<1.50$  GI/L) (based on 3 test results as specified in Section 10.3.3.1) - AND - an infection that is not fully resolved.
- Total WBC count  $<2000$  cells/ $\mu\text{L}$  ( $<2.00 \times 10^3/\mu\text{L}$  or  $<2.00$  GI/L).
- Lymphocyte count  $<200$  cells/ $\mu\text{L}$  ( $<0.20 \times 10^3/\mu\text{L}$  or  $<0.20$  GI/L).
- Platelet count  $<50,000$  cells/ $\mu\text{L}$  ( $<50 \times 10^3/\mu\text{L}$  or  $<50$  GI/L).
- Discontinuation due to a hepatic event or liver test abnormality: discontinuation of the investigational product for abnormal liver tests should be considered by the investigator when a study patient meets one of the following conditions, after consultation with the Lilly designated medical monitor (clinical research physician [CRP] or clinical research scientist [CRS]):
  - ALT or AST  $>8\text{X}$  ULN
  - ALT or AST  $>5\text{X}$  ULN for more than 2 weeks
  - ALT or AST  $>3\text{X}$  ULN and total bilirubin level (TBL)  $>2\text{X}$  ULN or international normalized ratio (INR)  $>1.5$
  - ALT or AST  $>3\text{X}$  ULN with the appearance of fatigue, nausea, vomiting, right upper-quadrant pain or tenderness, fever, rash, and/or eosinophilia ( $>5\%$ )
  - Alkaline phosphatase (ALP)  $>3\text{X}$  ULN
  - ALP  $>2.5\text{X}$  ULN and TBL  $>2\text{X}$  ULN
  - ALP  $>2.5\text{X}$  ULN with the appearance of fatigue, nausea, vomiting, right quadrant pain or tenderness, fever, rash, and/or eosinophilia ( $>5\%$ )

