#### **10.3.2.2. Chest X-Ray and Tuberculosis Testing**

A posterior-anterior view chest x-ray will be obtained, unless the x-ray or results from a chest x-ray obtained within 6 months prior to the study are available. The chest x-ray or results will be reviewed by the investigator or designee to exclude patients with active TB infection.

In addition, patients will be tested at screening as indicated on the Study Schedule ([Attachment 1](#)) for evidence of active or latent TB (positive PPD [ $\geq 5$ -mm induration] or positive QuantiFERON®-TB Gold test/T-SPOT®.TB at screening but no other evidence of active TB). In sites where sample collection and proper incubation for the QuantiFERON®-TB Gold test are

available at the site and in the judgment of the investigator preferred as an alternative to the PPD skin test for the evaluation of TB infection, it may be used instead of the PPD test (positive test excluded) and would be sent to central lab for testing. If the QuantiFERON®-TB Gold test is indeterminate, 1 retest is allowed. If the retest is indeterminate, the patient will be excluded from the study. If the retest is positive but without clinical evidence of TB, the patients will be considered as latent TB for study purpose.

Patients with documentation of a negative test result within 3 months prior to baseline (Week 0; Visit 2) do not need a TB screen at Visit 1. Documentation of this test result must include a record of the size of the induration response. A PPD test recorded as negative without documenting the size of induration will result in a retest.

However, patients with a PPD skin test  $\geq 5$  mm induration or a positive QuantiFERON®-TB Gold or positive T-SPOT®.TB test at screening, but no other evidence of active TB may be rescreened 1 time and may be enrolled without repeating a PPD or QuantiFERON®-TB Gold or T-SPOT®.TB test if the following conditions are met:

- after receiving at least 4 weeks of appropriate latent TB infection (LTBI) therapy,
- with no evidence of hepatotoxicity (ALT/AST must remain  $\leq 2$  times ULN) upon retesting of serum ALT/AST prior to randomization. Such patients must complete appropriate LTBI therapy during the course of the study in order to remain eligible, and
- meet all other Inclusion/Exclusion criteria for participation.

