### Hepatic Safety Data Collection

Additional safety data should be collected via the eCRF if 1 or more of the following conditions occur:

- elevation of serum ALT to  $\geq 5X$  ULN on 2 or more consecutive blood tests
- elevated serum TBL to  $\geq 2X$  ULN (except for cases of known Gilbert's syndrome)
- elevation of serum ALP to  $\geq 2X$  ULN on 2 or more consecutive blood tests
- patient discontinued from treatment due to a hepatic event or abnormality of liver tests
- hepatic event considered to be a SAE

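### The 3-to-5-day liver retest and follow-up monitoring in Protocol 10.3.3.2 start on ALT, ALP or total bilirubin but not on AST, although AST above 5X ULN for more than two weeks is a ground to consider stopping treatment

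*Protocol*

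**What the plan says.** Protocol 10.3.3.2 sets the retest rule. It begins "If a study patient experiences elevated ALT" at 3X ULN or more, and continues with ALP at 2X ULN or more and total bilirubin (TBL) at 2X ULN or more. When any of these is met, liver testing "should be repeated within 3 to 5 days including ALT, AST, ALP, TBL, direct bilirubin", plus gamma-glutamyl transferase and creatine kinase. If the abnormality persists or worsens, clinical and laboratory monitoring follows, and ALT, AST, TBL and ALP are tracked until they normalise or return to about baseline. AST is thus in the repeat panel and in the monitoring, but not among the triggers.

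Section 8.3.1.1 does name AST. Stopping treatment "should be considered by the investigator when a study patient meets one of the following conditions", after consultation with the medical monitor. One condition is ALT or AST above 5X "ULN for more than 2 weeks". The others that name AST are above 8X ULN, above 3X ULN with raised TBL or INR, and above 3X ULN with listed symptoms and/or eosinophilia.

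The Hepatic Safety Data Collection rule, in the same part of Section 10.3.3, starts with "elevation of serum ALT to" 5X ULN or more on consecutive tests, again without AST. It also collects data for any "patient discontinued from treatment due to a hepatic event or abnormality of liver tests" and for hepatic SAEs, whichever enzyme is involved.

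**The concern.** A stopping condition based on duration needs at least two values. For ALT, Section 10.3.3.2 provides a prompt second value and then opens monitoring. For AST alone it provides neither, although Section 8.3.1.1 gives both enzymes the same condition. Followed literally, a patient with a substantial isolated AST rise could go to the next scheduled chemistry panel before anyone is obliged to confirm it or to start tracking it.

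What is at stake is the timeliness of safety follow-up for an uncommon laboratory pattern. No efficacy estimate or test is affected.

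**Working it through.** The plan states no figure on this point, so the check applies its rules to cases and reads the gaps off its schedule.

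**1. Retest rule applied to an isolated AST rise.** From Section 10.3.3.2, retest = (ALT ≥3X) or (ALP ≥2X) or (TBL ≥2X ULN). Set ALT, ALP and TBL to 1X ULN, assume no symptoms, eosinophilia or raised INR, and vary AST:

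| AST (X ULN) | 3-to-5-day retest? | Section 8.3.1.1 |
|---|---|---|
| 3.5 | no | no condition met |
| 5.5 | no | met only if it lasts more than 2 weeks |
| 7.9 | no | met only if it lasts more than 2 weeks |
| 8.5 | no | met on one value |

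The retest is missing for every isolated AST value. It matters most above 5X and up to 8X, where the condition turns on duration and so needs a later value.

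**2. When the next AST is scheduled.** AST is part of serum chemistry (Attachment 2). Attachment 1 schedules serum chemistry from Week 12 at Weeks 12, 16, 20, 24, 32, 40, 48 and 60. The nominal gap is the difference in study days; the range adds or subtracts both visit windows (±4 days at Week 12, ±7 days afterwards).

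| Interval | Nominal gap | With windows |
|---|---|---|
| W12–16 | 112 − 84 = 28 days | 28 ± 11 = 17 to 39 |
| W16–20, W20–24 | 28 days each | 28 ± 14 = 14 to 42 |
| W24–32, W32–40, W40–48 | 56 days each | 56 ± 14 = 42 to 70 |
| W48–60 | 420 − 336 = 84 days | 84 ± 14 = 70 to 98 |

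An AST rise found at one of these draws has its next scheduled value nominally 28 to 84 days later (4 to 12 weeks). Measured from the 5-day outer limit for ALT, that is 28 − 5 = 23 to 84 − 5 = 79 days later. Even the shortest interval the windows permit, 14 days, lies outside 3 to 5 days.

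**3. Is a dated AST recheck required elsewhere?**

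- Section 10.3 makes the investigator responsible for following serious or medically important events, but leaves the frequency to the investigator.
- Section 10.4.1 requires documented review of each laboratory safety report and permits extra samples.
- Attachment 2, footnote b, permits unscheduled chemistry.
- Attachment 3 lists hepatic tests that may be done, with no AST threshold and no time limit.
- Section 10.3.3 (periodic sponsor review) and Section 12.2.10.1 (DMC review) set no retest time for an individual patient.

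Each makes a recheck possible. None gives it a date.

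**The case against.** The strongest reply is that the gap is narrow and well guarded. Section 8.3.1.1 already acts on AST above 8X ULN from one value, and on AST above 3X ULN with symptoms, eosinophilia, raised TBL or raised INR, with no duration requirement. Investigators must review every laboratory report, may draw unscheduled chemistry, and are reading a protocol whose own persistence condition names AST. The ALT retest is itself worded as something that should happen. All of this stands. It confines the point to an asymptomatic, isolated rise and makes it modest, but it does not supply a date.

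Three stronger readings are tempting and are not supported.

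- *That the retest would supply the two-week value.* A repeat at 3 to 5 days cannot show persistence beyond two weeks, and Section 10.3.3.2 gives no interval for the monitoring that follows. ALT has no dated value at two weeks either. Adding AST would start confirmation and monitoring, no more. For the same reason, the number of scheduled gaps longer than two weeks does not measure harm: a draw at four weeks can show persistence, and a draw at one week cannot.
- *That dosing continues because AST was left out.* Section 10.3.3.2 does not hold dosing pending the retest for any analyte.
- *That the documents otherwise treat the two enzymes alike, so this must be an oversight.* They are paired in places: eligibility uses "Aspartate aminotransferase (AST) or alanine aminotransferase (ALT") above 2.5X ULN, and patients on latent TB therapy need a check "upon retesting of serum ALT/AST prior to randomization". But the hepatic eCRF rule uses ALT without AST, as do the SAP's combined elevated hepatic criteria and its eDISH plot (Table RHBH.6.8). An ALT-based convention is a possible explanation, and the documents do not say which it was.

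**Conclusion.** The concern holds in a limited form. The retest trigger is narrower than the discontinuation conditions: Section 8.3.1.1 can rest on AST alone, while Section 10.3.3.2 cannot be started by it. For an asymptomatic isolated AST of 5X to 8X ULN, with ALT below 3X, ALP and TBL below 2X, and no eosinophilia or raised INR, no dated confirmation exists. After Week 12 the next scheduled value is nominally 4 to 12 weeks away.

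This rests on reading the trigger sentence literally and on the nominal schedule in Attachment 1. The documents give no rate for this pattern, so no number of affected patients can be stated. It is a low-cost improvement to safety follow-up, not a defect in the trial's inference.

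**What to change.** Two wording changes:

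1. In Section 10.3.3.2, change the first trigger to **ALT or AST ≥3X ULN**, with the medical team confirming the AST threshold.
2. In the Hepatic Safety Data Collection list, change the first item to **ALT or AST ≥5X ULN** on at least two consecutive tests.

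No new assay is needed, because AST is already on every chemistry panel. The cost is a few extra repeat samples and visits. Some will be for AST of non-hepatic origin, which the creatine kinase already in the repeat panel helps to identify.
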